10.3.2 By Segment Analyses

(This provides the opportunity to include lesion, segment and vessel characteristics unique to each lesion and segment in multivariate analyses).

- a) *By segment, change in MLD of all study endpoint segments.* The change is adjusted for the actual time interval between the entry arteriogram and the follow-up arteriogram(s).
- b) *By segment, change in the mean (rather than minimum) lesion diameter of all endpoint segments.* The mean segment diameter extends over a segment length that is identical on the entry and exit angiogram.
- c) *By segment, change in the mean diameters of all non-disease containing segments (no lesion \geq 15% on either the entry or exit angiogram).* The mean segment diameter extends over a segment length that is identical on the entry and concluding angiogram. Segments included in this analysis must be in the main coronary vessels or their major branches and at least 1.5 mm in diameter.
- d) *By segment, change in the mean diameters of quantitated segments.* This includes both study endpoint segments and quantitated segments with no lesion \geq 15%. The segments included in this analysis must be in the main coronary vessels or their major branches, and must be at least 1.5 mm in diameter. The mean segment diameter extends over a segment length that is identical on the entry and concluding angiogram.

10.3.3 Additional Analyses

- a) *Study of lesions >75%*: change in the, by patient, average of the MLD of all segments containing >75% stenosis on the entry angiogram. The change is adjusted for the actual time interval between the entry arteriogram and the follow-up arteriogram. Many of these segments may become subject to catheter based or surgical interventions during the course of the study.

- b) *Study of post PTCA restenosis*: change in the MLD of any stenosis having catheter interventions from the immediate post PTCA procedure to the exit angiogram. All lesions that were treated within 6 weeks prior to or during the entry angiographic procedure are included in this analysis. However, there must be at least a 6-month, in study, interval between the interventional procedure and the follow-up angiogram which may be either a protocol mandated, concluding angiogram or a clinically indicated intercurrent angiogram. The primary analysis for this study will be based on the one lesion per patient that shows the greatest change from initial eligibility to follow-up. A second analysis will consider each PTCA treated lesion as an individual statistical entity. Both of these analyses will include the type of catheter-based intervention along with multiple other standard angiographic lesion characteristics as covariates.

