3.2 INCLUSION CRITERIA

To be eligible for randomization, women must:

1. Be postmenopausal by one of the following criteria:
 - a. Have had a bilateral oophorectomy at any age,
 - b. Be ≥ 55 years of age (or have an FSH ≥ 40 , if under age 55)
 - c. $<$ age 55 and FSH ≥ 40

Women under 45 years of age without a bilateral oophorectomy, or FSH ≥ 40 are excluded.

2. Have a WAVE protocol angiogram performed within four months of randomization, while hemodynamically stable, demonstrating at least one vessel segment with a 15-75 percent stenosis. The qualifying artery may not have been intervened (dilated, atherectomized or stented). If the angiogram was performed within 2 weeks of a myocardial infarction, the qualifying segment may not be the infarct segment.
3. Provide signed informed consent.

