7.3 RANDOMIZATION

Women who have met all inclusion criteria and have none of the exclusion criteria, and who have signed the informed consent, will be scheduled for a randomization visit. Prior to the randomization visit all women who did not have a blood collection at the screening visit will be advised to fast for at least twelve hours prior to the visit. A blood sample will be collected for central analysis and a local sample for assessment of INR if needed. Data to be collected are indicated in Table 2.

Randomization to one of the four possible study groups (active HRT and placebo antioxidants, active HRT and active antioxidants, placebo HRT and active antioxidants, placebo HRT and placebo antioxidants) will be by a telephone call to the Study Coordinating Center. After confirmation of the patient's eligibility the SCC will issue a

unique patient identifier and medication codes that the clinical center coordinator will use to obtain the woman's study medications. The unique patient identifier will be used on all study forms, laboratory samples, angiograms and any other necessary study documents. Each woman will have a one in four chance of being assigned to each of the four study groups. Randomization will be stratified by clinical center (n=5) and by whether a hysterectomy has been performed. Each woman will be given a seven month supply of her study medications, a medication instruction sheet, a bleeding calendar for those women with a uterus, a bottle of Centrum Silver vitamins (if she requests it), and an appointment for the one month visit.

TABLE 2

WAVE Summary	Screening	Randomization	IM	3M	6M	12M	18M	24M	30M	36M	Exit
Consent	X										
Creat, trig, FSH (if needed)	X										
INR	Obtain at either visit		X								
Study Bloods	Obtain at either visit			X			X			X	
Ht/wt, BP, waist/hip	Obtain at either visit					X		X		X	
Randomization form		X									
Breast, pelvic, Pap, mamm, breast self-exam teaching	X					X		X		X	
Sign medical release	X					X		X		X	
Brachial reactivity	Obtain between consent and initiation of study medication			X							
Dipyridamole SPECT/ETT				X						X	
ECG		X				X				X	
Patient tracking form		X			Update as needed						
Bleeding calendar		X	X	X	X	prn	prn				
Dispense study meds		X			X	X	X	X	X		
Adherence assessment					X	X	X	X	X	X	X
Quality of Life		X		X			X		X		
Follow-up visit*					X	X	X	X	X	X	X
Angiogram	X										X
Physical exam		X				X		X		X	

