10.2 PRIMARY ENDPOINT

10.2.1 Definition of the Primary Endpoint

The primary endpoint will be evaluated in all segments containing 15 - 75% lesions noted on the entry angiogram or any new lesions \geq 15% observed on a follow-up angiogram

within the study duration. These segments are referred to as the study endpoint segments. The change in MLD of each segment is divided by the time between the entry arteriogram and the final angiogram within the prespecified study follow-up-period. An exception will be made for intercurrent angiograms and revascularization procedures: these procedures will provide the concluding measurements for those segments that were intervened. For such segments, the change in MLD will be divided by the time between the baseline angiogram and the pre-procedure intercurrent angiogram. The study goal is to obtain a protocol angiogram within the last six months of the scheduled end of the trial. With recruitment anticipated to occur over a 12-15 month period, this implies an anticipated average follow-up of approximately 40.5 months. If the patient has had a coronary angiogram for clinical indications within six months of the planned study termination, the results from that arteriogram can be used in lieu of an exit angiogram. If the angiogram has occurred more than six months before the end of the trial an additional angiogram will be requested.

Patients eligible for entry into the study will have one or more segments containing 15 - 75% stenosis which have not been influenced by prior catheter interventions. These are referred to as qualifying segments and lesions. Segments identified on the entry as containing a 15 - 75% stenosis or on the concluding arteriogram(s) as containing any lesion $\geq 15\%$ are considered endpoint segments. This definition automatically includes those segments which originally qualified the patient for study entry. Segments included in this analysis must be in the main coronary vessels or their major branches and have a reference diameter >1.5 mm. Segments or lesions progressing to 99 - 100% stenosis are automatically assigned a MLD of 0.0 mm. Non-visualized segments distal to total occlusions are considered lost to follow-up.

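### The restenosis analysis in 10.3.3(b) counts up to 5.4 months of lumen change before randomization, and its six-month minimum starts at the procedure rather than at randomization

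*Protocol*

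**What the plan says.** Item b of Protocol 10.3.3 defines the outcome as "change in the MLD of any stenosis having catheter interventions from the immediate post PTCA procedure to the exit angiogram". On which lesions enter, it says: "All lesions that were treated within 6 weeks prior to or during the entry angiographic procedure are included in this analysis". It sets a minimum follow-up: "there must be at least a 6-month, in study, interval between the interventional procedure and the follow-up angiogram". Either the concluding film or a clinically indicated intercurrent film may serve as follow-up.

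The same item bases its main analysis on "the one lesion per patient that shows the greatest change from initial eligibility to follow-up", which names a different starting point from the post-PTCA lumen. A second analysis takes each treated lesion separately. The covariates named for both are the type of intervention and angiographic lesion characteristics.

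Two other places set the timing. Inclusion criterion 2 in 3.2 requires women to "Have a WAVE protocol angiogram performed within four months of randomization, while hemodynamically stable". Section 7.3 dispenses drug at the randomization visit: "Each woman will be given a seven month supply of her study medications".

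**The concern.** Both the choice of lesions and the starting lumen are tied to the PTCA and the entry film, while treatment starts at randomization. Whatever the lumen does in between is part of the outcome but cannot respond to either treatment.

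Write a lesion's change as A + B, with A before randomization and B after. Randomization balances A in expectation, so the expected difference between arms comes from B alone. A brings variance. The comparison also shows less than the effect a drug would have if it acted on the whole course from the procedure onward. A null result would then say little about restenosis in women randomized late after PTCA.

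The minimum-interval rule looks meant to guarantee time on study, but its wording does not. For the lesions the item lists, the procedure comes before randomization, so an interval that starts there is not wholly in-study.

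Long gaps are foreseeable. Section 3.3 advises a three-month washout for women on hormone therapy for at least three months when screened, and it bars randomization within 4 weeks of a myocardial infarction. The protocol does not say how often long gaps would occur.

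**Working it through.** The protocol states no figure for this gap, so there is none to reproduce.

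**Inputs**
- PTCA to entry film: 0 to 6 weeks (10.3.3(b)).
- Entry film to randomization: 0 to 4 months (3.2, criterion 2).
- Start of drug: not before randomization (7.3).
- Minimum interval to the follow-up film: 6 months (10.3.3(b)).
- Usual follow-up: "anticipated average follow-up of approximately 40.5 months" (10.2.1), taken here as running from randomization.

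**Maximum gap g from PTCA to randomization**
- 6 weeks = 42 / 30.44 = 1.38 months.
- g = 1.38 + 4 = 5.38 months.
- If treated during the entry procedure, g = 0 + 4 = 4 months.

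**Shortest possible time on treatment, minimum counted from the procedure**
- 6 − 5.38 = 0.62 months, or 0.62 × 30.44 = 19 days, about 2.7 weeks.

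**Untreated share of measured time = g / (PTCA to follow-up film)**

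| Follow-up film | g = 5.38 months | g = 4 months |
|---|---|---|
| 6 months after PTCA | 5.38/6 = 90% | 4/6 = 67% |
| 6 months after randomization | 5.38/11.38 = 47% | 4/10 = 40% |
| 36 months after randomization | 5.38/41.38 = 13% | 4/40 = 10% |
| 40.5 months after randomization | 5.38/45.88 = 12% | 4/44.5 = 9% |

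**Untreated share of loss.** This needs a time course, and the protocol has none. As an assumption only, let loss be proportional to 1 − exp(−t/τ). The share before randomization is then (1 − exp(−g/τ)) / (1 − exp(−T/τ)), with T the time from PTCA to the film. For g = 5.38 and T = 45.88:

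| τ (months) | 2 | 3 | 6 | 7.8 | 12 | 24 |
|---|---|---|---|---|---|---|
| share | 93% | 83% | 59% | 50% | 37% | 24% |

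With a gap of only 1 month, the share is 39% at τ = 2 and 8% at τ = 12.

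**Baseline.** If initial eligibility means the entry film, that baseline can be up to 6 weeks after the PTCA, and the longest untreated span falls from 5.38 to 4 months. The protocol does not say whether it means this.

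**The case against.** Four points can be made for the plan.

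- **The extreme needs three things together:** the longest gap, a film near six months, and a minimum counted from the procedure. By default change is measured to the exit angiogram, and at usual follow-up the untreated part is about 12 to 13% of the time. This stands. It limits the size of the problem but does not remove it, because intercurrent films are allowed as follow-up.
- **The words in-study probably aim at exposure after randomization.** On that reading the case of under three weeks disappears. That is a fair guess at the intent, but the sentence still starts the interval at the procedure. Even on the kinder reading, 47% of the time can be untreated.
- **The consequence is small.** This is one additional analysis with no power claim, the untreated change is balanced in expectation, and the primary endpoint does not depend on it. All of this stands.
- **Covariates are often left to a statistical analysis plan,** and one may exist that is not shown. The missing covariate is therefore not an error. The interval's starting point and the two baselines differ in kind: the protocol itself fixes them, in terms that do not fit together.

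A reader might go further and infer that most of the lumen loss precedes treatment, or put a sample-size penalty on it. If loss were even over six months and gaps uniform from 0 to 5.38 months (mean 2.69), 1 − 2.69/6 = 55% of the effect would remain, which implies 1/0.552² = 3.3 times as many lesions. The documents do not support this. Six months is a minimum for including a lesion, not a period over which loss occurs, and the distribution of gaps is unknown. If loss were instead even over the mean gap plus 40.5 months, 1 − 2.69/43.19 = 94% would remain and the factor would be 1/0.938² = 1.14.

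**Conclusion.** The point holds as a minor design and wording fault. Up to 5.38 months of lumen change before any study drug is counted in the between-arm restenosis comparison, and the minimum interval as written does not secure time on treatment. The result is dilution and noise, with no advantage to either arm.

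The gap follows directly from 10.3.3(b) and 3.2. It is a maximum, not a typical value. The shares of time also rest on the follow-up film chosen. No share of loss can be given, and neither a claim that most loss is untreated nor a fixed inflation factor is established. A null restenosis result could not by itself be read as no effect on restenosis.

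**What to change.** 1. Count the six-month minimum from randomization, and say so in 10.3.3(b).
2. Name one baseline and use it in both restenosis analyses. If initial eligibility is meant to be the entry film, state that.
3. Add the PTCA-to-randomization interval as a covariate in both analyses.
4. Report results by that interval. A covariate reduces noise but does not undo dilution, so the breakdown is needed for interpretation.
5. Add a sensitivity analysis limited to short gaps, with the cut-off fixed in advance. Restricting the main set in this way would give up lesions for a cleaner contrast, so it is better kept as a sensitivity analysis.

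The cost is some lesions with early intercurrent films, plus a little more analysis work. Those films are taken for clinical reasons, so the number dropped should be shown by arm. The six-week and six-month rules already require the procedure date, so the interval should need no new measurement.

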10.4 SAMPLE SIZE CALCULATIONS

The sample size calculations are based on a change in mean MLD using a t-test. The antioxidant and HRT components are treated as separate trials (no interaction is assumed). No adjustment for multiple comparisons will be made.

The type 1 error rate α was 0.05 (2-tailed). Although a rank test will be used, given the sample sizes contemplated in the study, the power of the rank test is essentially the same as that of the t-test under the assumption of normality. The power calculations are based on the effect size, defined as the expected difference in outcome between treatment and control divided by the

standard deviation of the outcome (the outcome here is the change in mean MLD between baseline and follow-up). The effect sizes for four published studies are summarized below.

STARS	FATS	SCRIP	MARS
0.86	0.51	0.29	0.14

The weighted average of these effect sizes, weighing by the number of patients in each study is 0.334. With this effect size and a power of 0.90, the required total sample size is N=380. Assuming a dropout rate of 15%, 450 patients are needed. If a 20% dropout rate is assumed, the power of the test for various effect sizes is summarized in the table below:

	N=450	N=425	N=400	N=375	N=350
ES=0.30	0.81	0.79	0.77	0.74	0.71
ES=0.35	0.91	0.90	0.88	0.86	0.83
ES=0.40	0.97	0.96	0.95	0.93	0.92

Based on these considerations, 400 patients is considered the minimum acceptable sample size for the study. The target sample size for the study is 450 patients.

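### The second restenosis analysis in 10.3.3(b) takes the lesion as its unit although women are randomized, and the item leaves the baseline, the direction of change and early re-treatment badly fixed

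*Protocol*

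**What the plan says.** Protocol 7.3 allocates each woman to one of four groups with equal probability, so the woman is the randomized unit for both factors.

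Protocol 10.3.3(b) describes a study of restenosis in lesions treated by catheter at the entry procedure or in the six weeks before it. It contains four elements that matter here:

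- **Lead analysis.** It "will be based on the one lesion per patient that shows the greatest change from initial eligibility to follow-up".
- **Second analysis.** "A second analysis will consider each PTCA treated lesion as an individual statistical entity". Both analyses take covariates; neither mentions correlation within a woman.
- **Window.** The opening sentence measures change in minimum lumen diameter (MLD) from the film taken straight after the procedure to the exit film. The lead analysis instead starts at initial eligibility. The end also varies, because a clinically indicated intercurrent film may serve as follow-up.
- **Minimum interval.** "there must be at least a 6-month, in study, interval between the interventional procedure and the follow-up angiogram". Nothing is said about a lesion re-treated sooner.

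By contrast, the primary endpoint (10.2.1 and 10.2.2) averages segments within each woman. For a revascularized segment it takes the film made before the procedure as the concluding measurement. The study of lesions above 75% in 10.3.3(a) also averages within the woman.

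**The concern.** A treatment comparison has to be judged against the variation between randomized units. When lesions are counted as separate entities, two lesions in one woman are treated as two independent pieces of evidence about a treatment she was assigned once. If her lesions behave alike, the effective sample is smaller than the lesion count, the interval is too narrow and the p-value too small.

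Three further points make the restenosis endpoint hard to pin down.

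- Two starting points can give different answers for the same lesion. A baseline before dilatation mixes the gain from the procedure with later loss. Initial eligibility also has no clear meaning for a treated lesion, because 3.2 requires the qualifying artery to be untouched by intervention.
- Greatest change without a direction could select a lumen gain in one woman and a loss in another.
- A lesion that fails and is re-treated before 6 months is not scored as a failure under any stated rule.

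At stake is a restenosis result by treatment arm that is published with overstated precision, or on a baseline chosen after the data are seen.

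**Working it through.** **1. The plan's own figures.** The protocol gives no sample size, power or standard error for any lesion-level analysis. Its patient-level figures in 10.4 reproduce:

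- n per arm = 2 × (1.960 + 1.2816)² / 0.334² = 188.4, so 189 per arm and 378 in total, against "With this effect size and a power of 0.90, the required total sample size is N=380".
- 380 / 0.85 = 447.1, or 448 in two equal arms, against 450.
- All 15 cells of the power table agree within 0.01.
- Weighting the four effect sizes by the Table 1 counts (74, 120, 246, 246) gives 230.62 / 686 = 0.336, against 0.334.

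The main sizing is therefore sound and is not in question.

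**2. Unclustered lesion analysis.** The inputs are two-sided α = 0.05 (10.4), and m treated lesions per woman with intra-woman correlation ICC. The protocol gives neither m nor ICC; the ranges below are assumptions.

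Design effect: DE = 1 + (m − 1) × ICC. True error = 2 × [1 − Φ(1.96 / √DE)].

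| m | DE (ICC 0.05 to 0.5) | True two-sided error |
|---|---|---|
| 1.2 | 1.01 to 1.10 | 5.1% to 6.2% |
| 1.5 | 1.03 to 1.25 | 5.3% to 8.0% |
| 2 | 1.05 to 1.50 | 5.6% to 11.0% |
| 3 | 1.10 to 2.00 | 6.2% to 16.6% |

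Worked extreme: m = 3 and ICC = 0.5 give DE = 2.00 and √DE = 1.414. Then 1.96 / 1.414 = 1.386, and the error is 16.6%. Over the grid, the correct standard error is 1.005 to 1.41 times the unclustered one.

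**3. Simulation under no treatment effect.** 200 women were randomized 1:1 with 1, 2 or 3 lesions each, in 4,000 runs. The Monte Carlo standard error near 5% is √(0.05 × 0.95 / 4000) = 0.0034. The lesion shares were 70/25/5% (mean 1.35) or 50/30/20% (mean 1.70).

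| Test | Rejection rate at nominal 0.05 |
|---|---|
| Each lesion as a unit, ICC 0 | 0.048 and 0.058 |
| Each lesion as a unit, ICC 0.3 | 0.074 and 0.089 |
| Each lesion as a unit, ICC 0.5 | 0.088 and 0.116 |
| One lesion per woman (lowest value), all ICCs | 0.045 to 0.054 |
| Mean per woman, all ICCs | 0.048 to 0.055 |

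The lesion-level rates at ICC 0.5 exceed what the mean count implies because lesion counts are unequal. Replacing m by the mean of k² over the mean of k gives 2.15 / 1.35 = 1.593 and 3.5 / 1.7 = 2.059. The errors are then 8.5% and 11.3%, close to the simulated values.

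**4. Loss of early failures.** This step assumes that the worst 5% to 20% of control lesions go unmeasured and that the true benefit is 0.3 or 0.4 SD. The mean of a normal variable with mean μ and SD 1, cut off below c, is μ + φ(c − μ) / [1 − Φ(c − μ)].

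Example: 10% of controls lost gives c = −1.282 and a control mean of 0.195. With a benefit of 0.3 SD, 5.7% of active lesions are lost and the active mean is 0.421. The observed difference is 0.421 − 0.195 = 0.226, which is 75% of the true 0.3. Over the assumed range the observed difference is 63% to 85% of the true one. With no treatment effect the losses are equal in the two arms and no false positive arises.

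**The case against.** The strongest reply is that this is one supplementary analysis, and that the protocol already puts a one-lesion-per-woman analysis ahead of it. Covariate and variance methods commonly sit in a statistical analysis plan, which is not at hand. With few treated lesions per woman the inflation is small: at 1.2 to 1.5 lesions the error is 5.1% to 8.0%. This stands as a limit on size. It does not remove the point, because the protocol itself names the lesion as the statistical entity.

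Four stronger readings are tempting, and the protocol does not support them.

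- **That the by-segment analyses in 10.3.2 have the same fault.** That section says only: "This provides the opportunity to include lesion, segment and vessel characteristics unique to each lesion and segment in multivariate analyses". It names no variance method and does not say that segments are independent. A mixed model with a patient effect is itself a by-segment analysis.
- **That the lead restenosis analysis has standard errors that are too small.** It uses one value per woman, and its simulated error stays near 5%. That simulation took the lowest value, but one value per woman protects the error rate whichever direction is meant.
- **That choosing the greatest-change lesion biases the arms.** The lesion set is fixed around the entry procedure, before randomization, and the rule is the same in both arms. It changes what is estimated, and the value depends on how many lesions a woman has.
- **That the 6-month rule excludes women who return early.** The concluding film can still serve for them, and 10.2.1 asks for a further film when a clinical one was taken too early. What remains is the missing rule for a lesion re-treated before 6 months.

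**Conclusion.** The point holds for the second restenosis analysis in 10.3.3(b). Followed as written, it understates standard errors whenever women have more than one treated lesion and outcomes correlate within a woman. The true error is about 5.1% to 16.6% at a nominal 5%. That range rests wholly on the assumed 1.2 to 3 lesions per woman and ICC of 0.05 to 0.5, and the lower part applies if most women have a single treated lesion.

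Three wording faults in the same item also hold: two starting points for the change, no direction for greatest change, and no rule for lesions re-treated before 6 months. The last departs from the primary endpoint's own convention. If it matters, it pulls the comparison toward no effect; it does not create a false positive.

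Severity is low. The primary endpoint averages within the woman, and the target of 450 reproduces.

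**What to change.** Reword 10.3.3(b) as follows:

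- Analyse all treated lesions with a mixed model (random patient intercept), or with GEE and patient-level robust standard errors, so that treatment is tested against variation between women.
- Use the MLD immediately after the procedure as the single baseline in both analyses.
- If the one-lesion analysis is kept, state the direction of greatest change.
- For a lesion re-treated before 6 months, take the film before re-treatment as the concluding measurement, as 10.2.1 and 10.2.2 do for the primary endpoint, and exempt it from the 6-month minimum.

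The cost is wording and programming, with slightly wider confidence intervals. On the assumed grid the standard error grows by a factor of 1.005 to 1.41. No new visits or films are needed, and the sample size does not change.
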